			case of failure to response.
			20. Section 11.4.6 Allowing out of
			window visits in case of UTI
			21. Section 13.2.3 change of per protocol
			definition threshold
			22. Section 13.2.4 deletion the definition
			of responder: will be part of the SAP
			23. Section 14.2.1 updating CEC responsibilities
			24. Section 18.9 update of contact
			person
			25. Section 18.10 update severity to
			comply with CTCAE common
			terminology
			26. Section 18.11 update of relationship
			to comply with MEDDEV
			27. Section 24 update of the study
			schedule with usability questions
			28. Update of voiding diary version 4
			, 3,
4	[name]	21-July-2019	1. Section 11.4.2
		-	a. addition of optional ultrasound
			during implantation visit
			b. Changing implantation visit
			window to (-)2 (+)3 weeks
	l		

Number	Revision / Date	Page
G02-CLP-0002_US	Rev. 08 / 27 July 2021	3 of 75

			c. Suture removal after 14 days
			d. Remove option to remove
			suture by the GP.
5	[name]	05-Jan-2020	1. Section 1 – update to be applicable to
3	[name]	03-Jan-2020	the US
			2. Sections 1, 4, 6.1, 10.1 and 13.1 –
			update indication for use to female with UUI.
			3. Sections 4, 5.2, 10.2.1, 10.6.2, 13.4
			and 13.5.8 – update sample size
			4. Section 4 and 10.2.1 – update
			number of sites to 35
			5. Sections 4 and 10.3.1 - update
			primary safety endpoint to include all AE's
			6. Sections 4 and 10.7 - updated
			inclusion/exclusion criteria
			7. Section 4 and 11.4 – update time
			window for implantation
			8. Section 4 and 13.5.4 – update
			hypothesis testing method to
			Clopper-Pearson
			9. Section 5.2 – update CE approval for OAB 2000
			10. Sections 10 and 14.2.2 – updated for
			staged enrollment provisions
			11. Sections 10.4.3 and 11.4.1 –
			clarification of documentation of
			concurrent medication.
			12. Section 11.4 – updated to allow
			phone visits and addition of device
			usage information
			13. Section 11.4.1 update handling of UTI
			at baseline.
			14. Section 11.4.2 update suture
			technique and material at
			implantation procedure.
			15. Sections 13.3, 13.2.2. and 10.8.1-
			update failure definition.
			16. Section 3 – adding UUI to acronym
			list.
			17. Section 6.3 – adding reference to the
			software version.

Number	Revision / Date	Page
G02-CLP-0002_US	Rev. 08 / 27 July 2021	4 of 75

20.	Subject Confidentiality	
21.	Termination of the Clinical Study	
22.	Insurance	
	II IOUI UI IOO	

Number	Revision / Date	Page
G02-CLP-0002_US	Rev. 08 / 27 July 2021	9 of 75

23.	Publication Policy	63
24.	Reporting Results on ClinicalTrials.gov	63
25.	Study Schedule	65
	,	
TAB	LE OF APPENDICES	
Apper	ndix 1 - BSW questionnaire	67
Apper	ndix 2 - MESA incontinence questionnaire	68
Apper	ndix 3 - OAB-q	70
	ndix 4 – PGI	
Vhhei	ndix 5 – PHQ-15	74
Apper	IIIIX 3 - FTQ-13	
Apper	ndix 6 – References	75

3. Acronym List

AE Adverse Event BL Baseline

BSW Benefit, Satisfaction and willingness to Continue questionnaire

CEC Clinical Event Committee
CIP Clinical Investigation Plan
CP Clinician Programmer
CRF Case Report Form

CTCAE Common Terminology Criteria for Adverse Events

DSMB Data Safety and Monitoring Board

FI Ethic Committee
Fi Fecal Incontinence
GCP Good Clinical Practice

HRQL Health Related Quality of Life IRB Institutional Review Boards

ITT Intend To Treat

MESA Medical, Epidemiological, and Social Aspects of Aging

MID Minimal Important Difference

MS Multiple Sclerosis
OAB Over Active Bladder

OAB-q Over Active Bladder questionnaire
OASIS Over Active bladder Stimulation System

PCB Printed Circuit Board

PPIUS Patient Perception of Intensity of Urgency Scale
PTNS Percutaneous/Posterior Tibial Nerve Stimulation
PGI-I Patient Global Impression of Improvement

PHQ-9 (or 15) Patient Health Questionnaire

PVR Post Void Residual
QoL Quality of Life
VD Voiding Diary

UADE Unanticipated adverse device effect

UUI Urinary Urge Incontinence

Number	Revision / Date	Page
G02-CLP-0002_US	Rev. 08 / 27 July 2021	11 of 75

4. Protocol Synopsis

FULL TITLE	A prospective study to assess the efficacy and safety of the BlueWind RENOVA iStim™ System in the treatment of patients diagnosed with overactive bladder (OASIS – OverActive bladder StImulation System study).	
RUNNING TITLE	BlueWind RENOVA iStim™ System for the treatment of OAB.	
STUDY INTENDED USE AND INDICATION FOR USE	The BlueWind Medical System is intended for peripheral nerve stimulation. The RENOVA iStim TM System is indicated for the treatment of women with symptoms of urgency incontinence alone or in combination with urinary urgency and/or urinary frequency.	
STUDY DESIGN	Prospective, interventional, multi-center, single arm, open label study.	
STUDY PURPOSE	To demonstrate efficacy and safety of BlueWind RENOVA iStim™ System therapy in the treatment of UUI.	
STUDY ARMS	Single arm. Device: RENOVA iStim™ System All subjects will receive active RENOVA iStim™ System treatment for the duration of the study.	
STUDY CONDUCT	 The study will consist of the following activities: Visit 1 - Screening Enrollment: Potential female subjects with UUI, who fulfil basic criteria will be informed of the study and will be invited to sign an informed consent form. Enrollment criteria will be verified against medical records and subject's interview. Baseline: Study candidates will be asked to fill out a 7- consecutive day voiding diary and a MESA incontinence questionnaire to determine predominant type of incontinence and a PHQ-15 questionnaire and a quality of life questionnaire (OAB-q). The diary and questionnaires will determine eligibility criteria and will serve as baseline data. Demographic information (age, race, height and weight, leg circumference), medical and surgical history and concomitant medication information will be collected. 	

Number	Revision / Date	Page
G02-CLP-0002_US	Rev. 08 / 27 July 2021	12 of 75

- Urine sample will be collected, blood will be drawn and a full physical examination, including a PVR measurement, will be performed.
- Once all eligibility criteria have been met and confirmed, implantation procedure will be scheduled.

☐ Visit 2 - Implantation

• 6 ± 4 weeks after starting the diary, eligible subjects will undergo unilateral implantation with the BlueWind RENOVA iStim™ System, during which intra-operative tibial motor or sensory response test will be performed.

☐ Visit 3 - Activation

 After a recovery period of 4-weeks (±2 weeks) post implantation, subjects will attend the clinic to undergo physical examination, urinalysis and parameter setting according to the individual patient sensations and will be trained on the use of the system. Therapy will be delivered for a minimum of 30 minutes and a maximum of 2 hours per day.

☐ Visits 4-8 – Treatment optimization and follow up

- Follow-up visits will be performed at 1, 3, 6, 9 and 12-months post activation.
- All follow-up visits will require completion of a voiding diary (a 3-day diary at 1, 3 and 9 months post activation and a 7-day diary at 6 and 12 months post activation) by the patient before coming to the visit. During the 6 and 12- months post activation follow-up visits quality of life (OAB-q), patient global impression of improvement (PGI-I) and Benefit, Satisfaction and Willingness to Continue (BSW) questionnaires will be collected.
- During each visit, stimulation parameters and level of treatment will be checked and adjusted as needed.
- At all follow up visits physical examination and collection of AE and concomitant medication will be performed
- Urine sample will be collected at each follow up visit
- Patients will be asked to complete usability questions

☐ Visits 9-12 – Long term follow-up

- Long term follow-up visits will be performed at 18, 24, 30, and 36-months post activation.
- If a subject already completed the 12-month follow-up visit and exited the study, she will be invited for a long-term follow-up consent visit in which, following her consent to participate, some eligibility criteria will be verified and treatment parameters setting will be performed. The subject will enter the visit schedule at the visit that aligns with her system activation date.
- If the subject discontinued treating herself after completion of the 12month visit, she will be asked to treat herself for 30 minutes, twice a day, for at least 4 weeks before arriving for her closest follow-up visit.

Number	Revision / Date	Page
G02-CLP-0002_US	Rev. 08 / 27 July 2021	13 of 75

COMMITTEES	 During this period, she will be asked to complete modified daily diary to capture incontinence episodes, time to treatment effect, and symptom improvement questions. Subjects continuing to the long-term follow-up will be asked to treat themselves per physician discretion but not less than twice a week for 30-minutes per treatment. All follow-up visits will require completion of 3-day voiding diary by the patient before coming to visit. Follow-up visits 9 (18-months) and 11 (30 months) will be performed by phone. Questions on treatment satisfaction will be asked, and any lifestyle, concomitant medication or OAB related changes from previous follow-up as well as any health issues will be addressed and documented. Visits may be performed in clinic if needed (i.e. treatment parameter adjustment, AE or device malfunction, etc. In such cases, the patient will arrive to the clinic and a visit similar to the 1, 3, and 9- months post activation will be performed. Follow-up visits 10 (24-months) and 12 (36-months) will be performed in clinic and will be similar to the 6 and 12- months follow-up visits Clinical Events Committee (CEC) Members will review and adjudicate safety information on an ongoing basis through the 12-month visit. Data Safety and Monitoring Board (DSMB) will conduct periodic independent reviews of the data and the reported adverse events, in order to ensure that an ongoing acceptable safety profile is maintained. A minimum of semi-annual meetings, or after about each new 50 subjects have been recruited is planned until all patients
	complete the 12-month visit and then a minimum of annual meetings thereafter until study completion.
NUMBER OF PATIENTS	150 subjects will be enrolled.
NUMBER OF CLINICAL SITES	Up to 30 sites.

Number	Revision / Date	Page
G02-CLP-0002_US	Rev. 08 / 27 July 2021	14 of 75

PRIMARY ENDPOINT	Efficacy	
	 Proportion of responders at 6 months post system activation as demonstrated by ≥50% improvement in average number of urgency related incontinence episodes, measured by 7-day Patient Voiding Diary. 	
	 Overall study success criteria are defined as a lower 97.5% confidence bound for a single binomial proportion of > 50% patient success at 6 months. Safety 	
	 Incidence of adverse events from implantation to 12-months post- activation. 	
SECONDARY ENDPOINTS	 Proportion of subjects with ≥10 points (MID) improvement compared to baseline in HRQL (based on OAB-q) at 6 months post system activation 	
	 Proportion of responders at 12 months post system activation as demonstrated by ≥50% improvement in either average number of urgency related incontinence episodes or average number of "large" (severe) urgency related incontinence episodes, as measured by 7-day Patient Voiding Diary. 	
	 Proportion of responders at 6 months post system activation as demonstrated by ≥50% improvement in the average number of moderate-severe urgency episodes PPIUS degree 3,4 or <8 voids/day 	
OTHER ENDPOINTS	The following endpoints will be assessed as other endpoints for the 6-, 12-, 24- and 36-months post activation, without formal hypothesis testing and type I error control.	
	Incidence of procedure or device related adverse events from 12- to 36- months post activation.	
	Patient Global Impression of Improvement (PGI-I) score.	
	Treatment Benefit, Satisfaction, and Willingness to Continue (BSW)	
	 Reduction in the average number of severe/large urgency related incontinence episodes. 	
	Improvement in OAB-q (HRQL and symptoms severity).	
	 Changes in the following OAB symptoms as measured by voiding diary compared to baseline: Reduction in the number of micturition episodes. Reduction in the number of urgency related incontinence episodes. Reduction in degree of urgency prior to void on Patient Perception of Intensity of Urgency Scale (PPIUS) from 0-4. Reduction in severity of incontinence episodes (amount leaked). 	

Number	Revision / Date	Page
G02-CLP-0002 US	Rev. 08 / 27 July 2021	15 of 75

 Proportion of dry subjects following treatment with the RENOVA iStim System as measured by 3 consecutive days of a patient voiding diary. Assessment of fecal incontinence symptoms in patients suffering from mixed fecal and urine incontinence. Patient compliance with treatment. Duration from treatment initiation to symptoms improvement (in subset of patients who stopped treatment after completing the 12 month visit and started again when consented for the long term follow-up). Assessment of treatment regimen Device usage
Subjects will be followed for 36 months after system activation. Overall study duration will be approximately 5 years.
 Signed written informed consent. Female aged 18 or greater (21 or greater in the US), with no plans to become pregnant during the trial; if of bearing potential, negative pregnancy test and if sexually active, using acceptable contraception. Subject who is mentally competent with the ability to understand and comply with the requirements of the study. Diagnosis of UUI demonstrated on 7-consecutive days voiding diary defined as a minimum of nine (9) leaking episodes associated with urgency, with at least one episode per day for 5 days More than or equal to 6 months history of UUI diagnosis Subject with inadequate response to any of the following conservative treatments (i.e. dietary restriction, fluid restriction, bladder training, behavioral modification, pelvic muscle training, biofeedback, etc.) and pharmacologic treatment. If used, subjects should be on stable dose of antimuscarinics and/or beta-3 adrenergic agonists for at least 3 months prior to baseline and agree to remain on stable medication consumption until the 12-month follow-up visit. If used, subjects should be on a stable dose of tricyclic antidepressants, Selective Serotonin Reuptake Inhibitors (SSRI) and Serotonin-Norepinephrine Reuptake Inhibitors (SNRI) for at least 3 months prior to baseline. Subjects with positive tibial nerve motor or sensory response tested via physical/neurological examination. Subjects with normal renal function defined by GFR of 50 ml/min or more Leg circumference of no less than 20 cm and no more than 30 cm at
 Leg circumference of no less than 20 cm and no more than 30 cm at implantation site (i.e. 5cm above the medial malleolus).

Number	Revision / Date	Page
G02-CLP-0002_US	Rev. 08 / 27 July 2021	16 of 75

	 Subject agrees to attend all follow-up evaluations and is willing and capable to completely and accurately fill out voiding diaries and questionnaires and is willing to complete required exams and tests. The following inclusion criteria will be re-evaluated for patients who completed 12-months follow-up and exited the study: Subject who is mentally competent with the ability to understand and comply with the requirements of the study.
EXCLUSION CRITERIA	1. Previous participation in another study with any investigational drug or
	device within the past 90 days.
	2. Subjects who are unable to operate the RENOVA iStim™ System
	Deemed unsuitable for enrollment by the investigator based on history or physical examination
	4. Subjects at high surgical risk with multiple illnesses or active general infections that expose them to excessive bleeding or delayed or non-healing wounds. This includes patients who need anticoagulation therapy that cannot be temporarily stopped for the implantation procedure
	 Any significant medical condition that is likely to interfere with study procedures, device operation, or likely to confound evaluation of study endpoints
	6. Subject has morbid obesity (>50 BMI)
	7. Any psychiatric or personality disorder at the discretion of the study physician
	8. PHQ-15 Patient Somatization Score ≥ 20
	 Any metal or other implant in the area of BlueWind RENOVA iStim™ implantation site (20cm distance).
	10. Variation in diuretics consumption within the last 6 months.
	11. Subjects who have received botulinum toxin injections within the past 12 months.
	12. Failure to respond to previous neuromodulation therapy for overactive bladder.
	13. Subjects who have received neurostimulation in the last 3 months.
	14. Previous urinary incontinence surgery or prolapse surgery using graft material within the last 12 months.
	15. Any spinal or genitourinary surgery within the last 6 months.
	16. Previous abdominoperineal resection of the rectum or previous radical hysterectomy.
	17. Skin, peripheral edema, orthopedic or neurologic anatomical limitations that preclude implantation or/and use of the device.
	18. Diagnosis of interstitial cystitis or bladder pain syndrome as defined by either American Urological Association (AUA) or European Association of Urology (EAU) guidelines.

Number	Revision / Date	Page
G02-CLP-0002_US	Rev. 08 / 27 July 2021	17 of 75

- 19. More than minimal level of suspected stress incontinence or mixed incontinence with stress component likely to confound study outcome, based on a 7-day voiding diary or medical history, or when stress incontinence score in the MESA incontinence questionnaire is higher than the urgency incontinence score.
- 20. Subjects with suspected urinary retention and/or PVR>150ml.
- 21. Any neurological disease or disorder including Alzheimer's, Parkinson, MS, stroke (CVI), neuropathy or injury resulting in neuropathy and/or suspected neurogenic bladder.
- 22. Current or recurrent urinary tract infection (3 or more infections in the last 6 months), or presence of urinary fistula, or urinary tract obstruction such as cancer, urethral stricture or presence of urinary stone.
- 23. History of chemotherapy or pelvic radiotherapy that might have affected bladder control or caused neuropathies (i.e. peripheral neuropathy)..
- 24. Diabetes with peripheral nerve neuropathy or severe uncontrolled diabetes (with HbA1C > 7%). Note: patients with HbA1C in the range of 7.1-7.5% may be considered eligible based on their complete medical record.
- 25. Uterine prolapse, cystocele, enterocele or rectocele with pelvic prolapse beyond the hymen.
- 26. Subjects with a documented history of allergic response to Platinum iridium, Titanium, Zirconia, Gold, Silicone or Parylene.
- 27. Other active implantable electronic device/s regardless of whether stimulation is ON or OFF.
- 28. Have a life expectancy of less than 1 year.
- 29. Subjects who are breastfeeding.
- 30. History of drug or alcohol abuse.

The following exclusion criteria will be re-evaluated for patients who completed 12-months follow-up and exited the study:

- 1. Subject whose RENOVA iStim implant has been removed.
- 2. Recent participation in another study with an active treatment arm within the past 90 days.
- 3. Subjects who are unable to operate the RENOVA iStim™ System
- 4. Deemed unsuitable for enrollment by the investigator based on history or physical examination
- Any significant medical condition that is likely to interfere with study procedures, device operation, or likely to confound evaluation of study endpoints
- 6. Any psychiatric or personality disorder at the discretion of the study physician

Number	Revision / Date	Page
G02-CLP-0002_US	Rev. 08 / 27 July 2021	18 of 75

- Subjects who have received botulinum toxin injections within the past 12 months.
 Subjects who have received any neuromodulation therapy in the last 3 months or implanted with any neuromodulation device
 Previous urinary incontinence surgery or prolapse surgery using graft material within the last 12 months.
- 10. Any spinal or genitourinary surgery within the last 6 months.
- 11. Previous abdominoperineal resection of the rectum or previous radical hysterectomy.
- 12. Diagnosis of interstitial cystitis or bladder pain syndrome as defined by either American Urological Association (AUA) or European Association of Urology (EAU) guidelines.
- 13. Subjects with suspected urinary retention and/or PVR>150ml.
- 14. Any neurological disease or disorder including Alzheimer's, Parkinson, MS, stroke (CVI), neuropathy or injury resulting in neuropathy and/or suspected neurogenic bladder.
- 15. Current or recurrent urinary tract infection (3 or more infections in the last 6 months), or presence of urinary fistula, or urinary tract obstruction such as cancer, urethral stricture or presence of urinary stone
- 16. History of chemotherapy or pelvic radiotherapy that might have affected bladder control or caused neuropathies (i.e. peripheral neuropathy).
- 17. Uterine prolapse, cystocele, enterocele or rectocele with pelvic prolapse beyond the hymen.
- 18. Other active implantable electronic device/s regardless of whether stimulation is ON or OFF.
- 19. Have a life expectancy of less than 1 year.
- 20. Subjects who are breastfeeding.

SAMPLE SIZE CONSIDERATION

Sample size calculation, based on the primary endpoint, yields a sample size of 114 patients. This calculation assumes an underlying response rate of 65%, the null response rate (performance goal) of 50%, with power of 90% and one-sided significance level of 0.025. To account for up to 15% attrition, a total of 134 subjects would be required. However, the total sample size of 150 subjects is driven by an important secondary objective that is expected to be evaluable in 70% of enrolled subjects: The proportion of responders at 6 months post system activation as

Number	Revision / Date	Page
G02-CLP-0002_US	Rev. 08 / 27 July 2021	19 of 75

	demonstrated by ≥50% improvement in the average number of moderate-severe urgency episodes PPIUS degree 3,4 or <8 voids/day. The assumed underlying response rate is 61%, with performance goal of 45%, 85% power and one-sided significance level of 0.025 yields a sample size of 89 subjects. To account for up to 15% attrition, 105 subjects are required to meet the criteria for this objective. Assuming 70% of enrolled subjects meet the criteria, a total of 150 subjects are required to be enrolled.
STATISTICAL ANALYSIS	For the primary endpoint, the lower 95% Clopper-Pearson confidence bound on the overall success rate will be calculated and compared to a pre-specified performance goal. Success on the primary analysis will be declared if the lower confidence bound is greater than the performance goal of 50%.

Number	Revision / Date	Page
G02-CLP-0002 US	Rev. 08 / 27 July 2021	20 of 75

5. Introduction

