10.3 Study Endpoints

10.3.1 Primary Endpoint

Efficacy

- Proportion of responders at 6 months post system activation as demonstrated by ≥50% improvement in average number of urgency related incontinence episodes, measured by 7-day Patient Voiding Diary.
 - Overall study success criteria is defined as a lower 97.5% confidence bound for a single binomial proportion of >50% patient success at 6 months

Safety

• Incidence of adverse events from implantation to 12-months post-activation.

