13.2 Analysis Sets

13.2.1 Safety and Efficacy Analysis Population – Intent To Treat (ITT)

The safety and effectiveness endpoints will be evaluated under principles of Intent to Treat (ITT). The analysis set will consist of all subjects for whom the implantation of the BlueWind RENOVA iStim™ system was attempted. Specifically, the analysis set will consist of all subjects for whom skin incision time was not missing.

Treatment of missing values:

- Subjects missing data "not in random" will be imputed "failure" on dichotomous endpoints
- "Failures" (not MAR) include:
 - Subject leaves the study due to related AE
 - Device explant
 - Lack of effect that results in significant increase of UUI medication
 - O Need for other 3rd line therapies for the management of UUI
- Baseline values will not be imputed
- Missing values in ITT not due to "failure" will be imputed using multiple imputation (MI).

Because MI assumes missing at random (MAR), sensitivity analyses will, as described below, be conducted to test the effects of other patterns of missingness. See Section 13.3 below for further discussing of how missing data will be handled in the efficacy analysis.

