13.3 Treatment of Missing Data for Efficacy Analyses

Frequency of missing data and the reasons for the missing data will be presented in the final report. For ITT effectiveness endpoints, a multiple imputation procedure will be used to impute missing endpoint data. Any patients missing endpoint data due to "failure" will be considered as a failure for the effectiveness analysis. Further sensitivity analyses will include, but may not be limited to, a tipping-point analysis for handling missing data.

Baseline variables included in the multiple imputation procedure may consist of:

- Age
- Number of UUI episodes per day
- OAB duration
- Number of prior attempted OAB treatments

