13.5.4 Primary Efficacy

For the primary analysis, the null hypothesis is that the response probability is less than or equal to 50%. We are interested in the alternative hypothesis that patients receiving the treatment have above 50% probability to achieve clinical improvement:

H₀: $\pi_{Renova} \le \pi_{PG}$ H₁: $\pi_{Renova} > \pi_{PG}$,

where π_{Renova} is the proportion of subjects meeting the pre-defined success criterion with RENOVA therapy (\geq 50% improvement in average number of urge related incontinence episodes), and π_{PG} is the prespecified performance goal (PG) of 50%.

Though sample size was conservatively calculated under an Exact Binomial test, the hypothesis testing will be conducted by constructing a two-sided, 95% Clopper-Pearson confidence interval. We will have succeeded in the trial if the lower bound of this confidence interval is above 50%.

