7.1 ITT population

Treatment of missing values:

- Subjects missing data "not in random" will be imputed as "failure" on dichotomous endpoints.
- "Failures" (not MAR) include:
 - Subject leaves the study due to related AE
 - Device explant
 - o Lack of effect that results in significant increase of UUI medication
 - Need for other 3rd line therapies for the management of UUI

Document ID	Revision / Date	Page
G02-CLP-0009	Rev. 06 / 18 May 2022	11 of 26

- Baseline values will not be imputed
- Missing values in ITT not due to "failure" will be imputed using multiple imputation (MI).

Multiple imputation will be applied to the primary and three secondary endpoints. The 'additional endpoint' analyses will not use multiple imputation. The imputation procedure will be performed on the continuous outcomes (e.g. number of incontinence episodes). Based on the imputed continuous outcome, the response will be defined accordingly for each endpoint.

The hypotheses will be tested by performing the logistic regression on each imputed dataset. Then SAS PROC MIANALYZE procedure will be used to calculate the combined confidence interval and the corresponding p-value. The evaluation on each endpoint will be successful if the lower limit of the confidence interval is above 50%. In addition, the primary analysis will present the observed frequency of responders and descriptive statistics of response rates over all imputed datasets.

Fifty (50) imputed datasets will be created (the seed is set to 123456).

The imputation will be done using covariates: Age, BMI, average number of urgency leaks, average number of urgent voids, HRQL score and OAB duration at baseline. This list might be reduced if the model fails to converge.

Because MI assumes missing at random (MAR), sensitivity analyses (i.e. tipping point) described below, will be conducted to test the effects of other patterns of missingness.

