12.6 Efficacy

12.6.1 Primary Efficacy Analysis

The following primary efficacy analyses will be carried out using the ITT population with multiple imputation as described in Section 7.1. The primary efficacy analysis will test the null hypothesis that the response probability on the primary efficacy endpoint is less than or equal to 50%. The alternative hypothesis for the primary analysis is that patients receiving the treatment have above 50% probability to achieve clinical improvement, as follows:

$$H_0: \pi_{Renova} \leq \pi_{PG}$$

$$H_1: \Pi_{Renova} > \Pi_{PG}$$

where π_{Renova} is the proportion of subjects meeting the pre-defined success criterion with RENOVA therapy (\geq 50% improvement in average number of urge related incontinence episodes, measured by a 7-day Patient Voiding Diary at 6 months post system activation), and π_{PG} is the prespecified performance goal (PG) of 50%.

Although sample size was conservatively calculated under an Exact Binomial test, the hypothesis will be tested by performing the logistic regression on each imputed dataset as described in Section 7.1. Then SAS PROC MIANALYZE procedure will be used to calculate the combined confidence interval and the corresponding p-value.

We will declare success on this endpoint if the lower limit of the confidence interval is above 50%.

Document ID	Revision / Date	Page
G02-CLP-0009	Rev. 06 / 18 May 2022	21 of 26

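### SAP 7.1 sets a 50% pass mark for an endpoint whose goal is 45%, SAP 9 pairs 114 subjects with the wrong power, and protocol and SAP name different primary tests

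*Protocol*

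**What the plan says.** **Performance goal.** SAP 7.1 states: "Multiple imputation will be applied to the primary and three secondary endpoints". Shortly afterwards it calls the evaluation of each endpoint successful if the lower confidence limit is above 50%. SAP 12.6.2 gives the three secondary endpoints their own goals: 50%, 50%, and 45% for the six-month urgency/frequency endpoint (at least 50% fewer PPIUS 3–4 episodes, or fewer than 8 voids per day). SAP 9, the protocol synopsis and protocol 13.4 all size that endpoint against 45%.

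**Power.** SAP 9 lists power of at least 80% among the inputs that lead to 114 evaluable subjects. The protocol synopsis gives 90% power for the same 114. Protocol 13.4 also lists at least 90%.

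**Primary test.** Protocol 13.5.4: "the hypothesis testing will be conducted by constructing a two-sided, 95% Clopper-Pearson confidence interval". SAP 12.6.1: "the hypothesis will be tested by performing the logistic regression on each imputed dataset as described in Section 7.1", with the results combined by PROC MIANALYZE. Neither SAP 7.1 nor SAP 12.6.1 gives the level of that interval. Protocol 13.3 says that "a multiple imputation procedure will be used to impute missing endpoint data", but the protocol does not say how a Clopper-Pearson interval is to be combined over imputed datasets.

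**Level and label.** The synopsis defines success by "a lower 97.5% confidence bound for a single binomial proportion", and protocol 10.3.1 does the same. The synopsis row on statistical analysis says "the lower 95% Clopper-Pearson confidence bound on the overall success rate will be calculated". Protocol 13.4 calls 134 evaluable; SAP 9 calls 114 evaluable and 134 enrolled.

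**The concern.** A single-arm trial judged against a performance goal rests on one rule: which interval, at which level, against which goal. Here each of those three elements is stated in more than one way in current text.

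The 50% sentence matters most. SAP 12.6.2 tests the secondary endpoints in the same way as the primary with respect to imputation, and SAP 12.6.1 refers to Section 7.1 for that method. A programmer who follows the references therefore arrives at the 50% sentence, and the endpoint affected is the reason for enrolling 150 rather than 134.

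The choice of test matters because the two methods can differ by a responder near the cut-off, and nothing I found in either document says which one governs.

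**Working it through.** **Inputs.** Primary: goal p0 = 0.50, assumed rate p1 = 0.65, one-sided α = 0.025 (protocol 13.4, SAP 9). Urgency/frequency secondary: p0 = 0.45, p1 = 0.61, one-sided α = 0.025, power at least 85%, 89 evaluable (SAP 9).

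**Methods.** Exact test: the cut-off r is the smallest count with P(X ≥ r | n, p0) ≤ 0.025; power is P(X ≥ r | n, p1). Stand-in for the SAP test: an intercept-only logistic model on complete data, with lower limit expit[ln(r/(n−r)) − 1.96·√(1/r + 1/(n−r))]. The SAP does not say that its model is intercept-only, so this is an assumption.

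**1. The plan's own figures reproduce.**
- Primary, 90% power: first n = 114, r = 68, exact size 2.44%, power 90.15%.
- Secondary, 85% power: first n = 89, r = 50, exact size 2.23%, power 85.1%.
- Attrition: 114/0.85 = 134.1; 89/0.85 = 104.7, so 105; 105/0.70 = 150.

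**2. Power input in SAP 9.** With the same inputs, exact power first reaches 80% at n = 90 (r = 55, power 81.2%). The listed 80% therefore does not lead to 114.

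**3. 50% applied to the urgency/frequency endpoint** (true rate 61%, no Hochberg adjustment):

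| Evaluable | Goal 45% | Goal 50%, logit | Goal 50%, exact |
|---|---|---|---|
| 89 | 50 needed, 85.1% | 54 needed, 57.1% | 55 needed, 48.5% |
| 105 (no attrition) | 58 needed, 90.4% | 63 needed, 62.4% | 64 needed, 54.7% |

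Example for 54 of 89: ln(54/35) = 0.4336; standard error √(1/54 + 1/35) = 0.2170; 0.4336 − 1.96 × 0.2170 = 0.0083; expit = 0.502, just above 50%. At the 45% goal the logit and exact cut-offs are the same (50 and 58).

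**4. Clopper-Pearson against logit, primary goal 50%, complete data.**
- Same cut-off at n = 114 (68), 134 (79) and 150 (88).
- For n = 100 to 150, the logit cut-off is one responder lower at 22 of 51 sizes, equal at 29, never higher.
- At those 22 sizes the one-sided size is 2.52% to 2.97%, against a design level of 2.5%. Example: n = 148, cut-off 86 against 87, size 2.9% against 2.0%.
- The effect of pooling over 50 imputed datasets was not computed.

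**5. Synopsis level, read literally as a one-sided 95% bound.** At n = 150 it passes at 86 responders (exact error 4.3%). The 97.5% bound needs 88 (2.0%).

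**The case against.** The case for leaving the text alone is that everything can be recovered. SAP 12.6.2 is the dedicated section and says that each endpoint is judged against its stated goal; 50% comes from one general sentence in the missing-data section. A 50% mark would also make success harder, so it cannot create a false positive. The SAP is later than the protocol, protocol section 13 leaves the detail to it, and SAP 12.6.1 openly contrasts exact sizing with the logistic test. Power of 90.15% literally satisfies at least 80%. The synopsis's lower 95% bound can be read as the lower limit of the two-sided 95% interval in protocol 13.5.4, which is the same as a one-sided 97.5% bound.

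Much of this stands. The synopsis level and the evaluable label are editorial, and 50% in SAP 7.1 is probably a sentence that was not adapted. Two things remain. SAP 7.1 is the section to which the test is referred, so its pass mark should not contradict SAP 12.6.2. And the SAP's acknowledgement covers the sizing method, not the fact that protocol 13.5.4 names a different test.

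A reader might also infer more than the documents support:
- *That the trial is underpowered for the primary endpoint because SAP 9 says 80%.* It is not: 114 gives 90.15%, and the 150 subjects are set by the secondary endpoint.
- *That the primary test runs at 4.3% error.* That needs the literal reading of one synopsis sentence, which the rest of the synopsis, protocol 10.3.1 and protocol 13.5.4 exclude.
- *That the SAP's test materially inflates error, or that it does not inflate it at all.* The complete-data stand-in shows a small excess at some sizes, 3.0% at most. The pooled test itself was not evaluated.

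**Conclusion.** The point holds as a consistency finding that should be fixed. There are three substantive errors.

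1. SAP 7.1's 50% for each endpoint contradicts the 45% goal. Followed literally, it would take the power of the endpoint that sets N from 85.1% to 57.1% (logit) or 48.5% (exact), at 89 evaluable and a 61% true rate. The loss arises only if SAP 7.1 is followed over SAP 12.6.2.
2. SAP 9's 80% does not produce 114; 90% does. The sample size is unaffected.
3. The protocol and the SAP name different primary tests, and the SAP gives no interval level for its own. The difference is at most one responder for n = 100 to 150, always in the lenient direction for the logit interval, with size up to 3.0%. This rests on complete data and an intercept-only model.

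The synopsis bound level and the label on 134 are editorial and carry little weight.

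**What to change.** - **SAP 7.1:** replace the 50% pass mark with a reference to the performance goal stated for each endpoint in Section 12.6.
- **SAP 9:** change the primary power input to at least 90%.
- **Protocol synopsis, protocol 13.5.4, SAP 7.1 and SAP 12.6.1:** name one primary test at two-sided 95% (one-sided 0.025), and state how it is combined over imputed datasets. The documents do not settle which test it should be. If the pooled logistic test is kept, specify the model, say that its size can slightly exceed 2.5%, and report the exact interval alongside it.
- **Editorial:** in the synopsis, describe the bound as the lower limit of the two-sided 95% interval (one-sided 97.5%). In protocol 13.4, call 114 evaluable and 134 enrolled, noting that 114/0.85 = 134.1, so 134 is rounded down.

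The cost is wording in both documents. Sample size, data collection and conduct do not change.
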